## **BACKGROUND**

Seizures in patients with epilepsy (ES) or with psychogenic nonepileptic seizures (PNES) are often severely disabling, difficult to treat, and are frequently encountered in neurology, psychiatry, and emergency departments. Epileptic seizures (ES) and PNES have the same appearance clinically, but have significantly different etiologies and treatments. Epilepsy is caused by abnormal brain cell discharges. PNES is a conversion disorder caused by trauma and stress and manifests neurologically with seizure-like episodes. Both types of seizures are common and disabling among Veterans and civilians. Up to 400,000 people in the U.S. have PNES. A quarter of the 80,000 Veterans with seizures have PNES. Many people with PNES are misdiagnosed with epilepsy and undergo invasive procedures and are prescribed anti-epileptic drugs (AEDs), which do not treat PNES.

Even though PNES have been described in the medical literature for millennia, effective treatments are limited. Based on a psychotherapy developed and studied for patients with epilepsy, in our treatment trials, we have developed and validated an innovative treatment, cognitive behavioral therapy (CBT) for PNES, which showed a significant reduction in PNES. Thus, we now can apply CBT to both, epilepsy and PNES, and call it CBT for seizures (CBT-Sz). Despite advances in understanding of the characteristics of patients with seizures, the neuropathophysiology of patients with PNES is less well understood. Understanding brain neurophysiology using neuroimaging in patients with seizure disorders will provide treatment targets for PNES/ES. This study will examine patients with epilepsy (ES) following head injury [i.e., posttraumatic epilepsy (PTE)] and posttraumatic PNES and will compare them to patients with traumatic brain injury (TBI) who do not have seizures.

## **OBJECTIVES**

We will investigate:

1. Differences in cerebral underpinnings of emotion and stress processing in PNES and PTE using well established fMRI probes.
2. Neuroimaging biomarker of PTE and PNES that predicts treatment outcome in order to inform effective non-pharmacologic treatments for seizures; and
3. Evidence for a positive treatment response to the intervention (CBT-Sz) that results in neuroplasticity – i.e., the symptom change instantiated by actual physiologic change in the brain.

## **STUDY DESIGN OVERVIEW**

Our plan is to investigate the cerebral underpinnings of emotion and stress processing in 88 individuals with confirmed PNES and 88 individuals with confirmed PTE and 88 individuals with a history of TBI without seizures (PNES or PTE) matched for psychiatric comorbidities (TBI control subjects – CS). In addition to the between group comparisons (PNES vs. PTE vs. CS), we will examine the changes in brains' response to fMRI probes after receiving treatment (CBT-Sz), a non-pharmacologic therapeutic approach that is used for the treatment of difficult to control seizures in patients with PNES and PTE. All participants in the 3 groups will receive fMRI scans at approximately 13 week intervals. Including CS in the neuroimaging and symptom surveys portion will allow us to determine the stability of signals between and within the individuals and to control for the effects of psychological and psychiatric comorbidities.

## **SPECIFIC AIMS**

**Specific Aim 1:** To compare neural correlates of response to fMRI stimuli before and after cognitive challenge (CBT-Sz). Individuals with PNES and PTE will be compared to individuals with a history of TBI who do not have PTE/PNES in order to control for common comorbidities including depression, anxiety and PTSD, and to show fMRI signal stability between and within the individuals.

**Hypothesis 1:** We hypothesize, based on our preliminary data, that baseline fMRI in all groups will show aberrant responses to stress and abnormal emotional processing between those with seizures vs. those without seizure disorders, with differences predominantly observed in the medial frontal cortices and amygdala with these differences being most abnormal in the PNES group.

**Specific Aim 2:** To investigate changes in neural circuitry for emotional processing in individuals with seizures after receiving CBT-Sz and to correlate these changes with symptomatic improvement.

**Hypothesis 2:** We hypothesize that CBT-Sz will lead to changes in the fMRI signals and in amygdala connectivity as shown with DTI and fMRI. This change will, in turn, be predicted by the magnitude of clinical responses defined by seizure frequency improvement over time and secondarily by targeted behavioral measures.

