Based on positive preliminary results, we conducted a multi-site randomized controlled trial (RCT), where 38 patients with video/EEG-confirmed, lone PNES were randomized to one of four treatment arms: Medication (sertraline) only, CBT-Sz only, CBT-Sz and Medication combined, or standard medical care (SMC). The CBT-Sz arm showed >50% seizure reduction ( $p < 0.01$  with 33% of the participants seizure-free at study exit), improvement in functioning and in scores on symptoms scales. The combined treatment arm also showed improvements in seizures and functioning while the Medication arm showed a trend for seizure improvement. SMC showed no seizure reduction or improvement in any secondary outcomes. Similarly, the workbook-based therapeutic approach (CBT-E) showed reduction in patients with epileptic seizures. Given that the intervention has been validated and manualized, successfully disseminated to other sites, used in multi-center studies, and that it reduces seizures and comorbidities, this is the most logical next step to investigate its ability to induce cortical plasticity and a potential biomarker for treatment response.

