### **3.0 Study Procedures**

#### **3.1 Study Design**

In this multi-site study, participants may be enrolled at PVAMC, RIH, and UAB. UAB will also receive referrals from BVAMC. This study aims to enroll 264 participants across the sites: 88 with PNES, 88 with PTE, and 88 with TBI without PNES or PTE. To meet recruitment goals, we will enroll both Veterans and civilians participants. Civilians will be seen at Rhode Island Hospital. All participants will be imaged at 2 time points and will complete self-reports, assessments and symptom measures as detailed in this protocol. The PNES and PTE participants will receive 12 sessions of CBT-Sz.

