### **3.6 Study intervention behavioral challenge (CBT-Sz)**

CBT-Sz will be given to 176 participants (88 with PNES; 88 with ES) by a trained therapist in 12 individual weekly one-hour sessions (the first CBT-Sz session is called the Introduction session, followed by 11 more sessions). Study sessions will be administered according to the manualized protocol. Participants will have weekly homework to complete between the sessions that may take up to 1 hour to complete. Missed CBT-Sz sessions will be made up, if possible, during the same week of the scheduled appointment or by scheduling the session the following week. If that is not possible, the session is counted as a missed appointment of the 12 sessions. The CBT-Sz therapist will document the missed sessions and report them to the research coordinator. Clinical experience suggests that the more appointments attended by the participant, the more response to the intervention. Participants will continue CBT-Sz sessions regardless of the number of missed sessions.

Participants who are unable to attend the CBT-Sz office appointments due to transportation limitations can have sessions over the telephone. The feasibility and safety of the tele-CBT has been demonstrated in our CBT-PNES trial and other CBT trials. Initial sessions, if possible, will take place in-person to establish patient-therapist rapport, and to provide the patient with the treatment packet (forms, modules, mailing envelopes, etc.) that will be used, if needed, in any future telephone sessions. If not, materials will be provided to participants at the baseline or 1st MRI visit. Tele-CBT follows the format and duration of face-to-face sessions and can be completed by any trained IRB approved study therapist at either the Providence VAMC, Rhode Island Hospital, and University of Alabama, Birmingham. Therapy sessions will be digitally recorded to ensure therapy adherence and competence.

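### Objective 3 and Hypothesis 2 credit change to CBT-Sz, but every seizure participant is planned to receive it and the only untreated group has no seizures; the wording and the test should be brought into line with Specific Aim 2

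*Combined protocol and SAP*

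**What the plan says.** **The causal wording.** Hypothesis 2 (Specific Aims) states: "We hypothesize that CBT-Sz will lead to changes in the fMRI signals and in amygdala connectivity as shown with DTI and fMRI". It adds that this change will be "predicted by the magnitude of clinical responses defined by seizure frequency improvement over time". Objective 3 seeks "Evidence for a positive treatment response to the intervention (CBT-Sz) that results in neuroplasticity", so it attributes symptom change as well as brain change to the therapy. Specific Aim 2, directly above Hypothesis 2, is milder: it looks at circuitry change following CBT-Sz and correlates it with improvement.

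**Who is treated.** Section 3.1 sets the groups as "88 with PNES, 88 with PTE, and 88 with TBI without PNES or PTE" and says "The PNES and PTE participants will receive 12 sessions of CBT-Sz". Section 3.6 confirms it: "CBT-Sz will be given to 176 participants (88 with PNES; 88 with ES) by a trained therapist". Groups are defined by diagnosis, and no random assignment is described.

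**Who is not treated.** The Study Design Overview gives the third group as "88 individuals with a history of TBI without seizures (PNES or PTE) matched for psychiatric comorbidities". Its stated purpose there and in Specific Aim 1 is to show signal stability and to control for comorbidity. By section 3.7, controls have two scans and assessments at baseline, endpoint and months 8 and 12. They have no therapy sessions, and so none of the homework, depression inventory or seizure-log review tied to those sessions.

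**The analysis.** Section 4.1 powers a related-samples t-test of pre- against post-intervention fMRI, then says 50 per group will allow within-group and between-group differences to be tested. The imaging analysis text in section 4 plans hierarchical linear models with covariates and a multiple-comparison correction. It names no group-by-time contrast as the test of Hypothesis 2. Section 4.3 asks people who do not start or finish CBT-Sz to have the second scan, so that completers and non-completers can be compared.

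**The concern.** To say that CBT-Sz causes brain or seizure change in people with PNES or PTE, one needs some view of what would have happened to such people without it. The plan has no group that supplies this. Any change that seizure participants would show over about 13 weeks anyway, or would show with any comparable therapist contact and monitoring, is counted with the effect of CBT-Sz.

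The controls help in part. They are rescanned at the same interval, so scanner drift, task habituation and practice can be subtracted so far as these are equal across groups. What is particular to having a seizure disorder, or to 12 weeks of contact, stays in. For seizure frequency, the first-named clinical response, the controls have nothing to compare. The seizure baseline is also one retrospective month followed by prospective weekly logs (section 3.7), so the method of recording changes as the study starts.

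At stake is the headline. Followed as written, a positive result would be reported as CBT-Sz producing neuroplasticity, which this design cannot show.

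**Working it through.** **1. What the power statement tests.** Inputs from section 4.1: d = 0.88, n = 14, two-sided 5%, stated power about 85%. Power is the probability that a noncentral t variable falls outside ±t(0.975, df).

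- Paired test: df = n − 1 = 13, noncentrality d√n = 0.88 × √14 = 3.29, critical value 2.160. Power = 86.0%, which reproduces the stated figure.
- Independent two-sample test, 14 v 14: df = 26, noncentrality d√(n/2) = 0.88 × √7 = 2.33. Power = 61.1%, which does not.
- The plan's more conservative case, paired, d = 0.65 and n = 25: noncentrality 0.65 × 5 = 3.25. Power = 87.6%, consistent with its statement that 25 should suffice.

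The sample-size argument therefore starts from a pre/post test within one group, with no control.

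**2. What each available contrast can separate.**

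| Contrast | Can remove | Leaves mixed with CBT-Sz |
|---|---|---|
| Pre v post within PNES or PTE | Stable differences between people | Rescan, practice, natural course, contact |
| Change in PNES or PTE v change in TBI controls | Rescan and practice, if equal across groups | Seizure-specific course, regression to the mean in seizure counts, 12 weeks of contact |
| Completers v non-completers (section 4.3) | Seizure diagnosis, if compared within diagnosis | Self-selection; numbers not given |
| Seizure frequency v controls | Not available | Everything |

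**3. Illustration of size.** The documents give no figure for non-specific change, so it is assumed. Let seizure participants shift by δ SD of change for reasons other than CBT-Sz, let controls not shift, let the SD of change be equal in the groups, and let CBT-Sz have no effect. Evaluable n is 88 × (1 − 0.20) = 70.4, taken as 70 per group. Tests are two-sided at 5%, without multiplicity correction.

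- Paired test: df = 69, noncentrality δ√70.
  - δ = 0: 5.0%
  - δ = 0.2: noncentrality 1.67, significant in 37.8% of trials
  - δ = 0.3: noncentrality 2.51, significant in 69.7%
- Change against controls, 70 v 70: df = 138, noncentrality δ√35.
  - δ = 0: 5.0%
  - δ = 0.2: noncentrality 1.18, significant in 21.7%
  - δ = 0.3: noncentrality 1.77, significant in 42.2%

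The control contrast reduces false attribution but does not return it to 5%.

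**4. Power given up by using the control contrast.** With the same formulas at 70 per group, the smallest difference detectable with 80% power is 0.34 SD of change for the paired test and 0.48 for change against controls. If the plan's d = 0.65 is taken to apply to the difference in change (an assumption), the control contrast still has 96.8% power.

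**The case against.** The strongest reply is that the plan already says most of what is wanted. Specific Aim 2 is associational, the Study Design Overview also speaks of change after treatment, and the controls are never offered as isolating CBT-Sz. This is a mechanistic study without randomisation, and what remains is causal verbs in one objective and one hypothesis. That stands as a limit on the remedy: it makes the fix small. It does not remove the point, because those two statements are what a result would be reported against, and section 4 does not name the controlled contrast as their test.

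Several stronger readings are tempting, and the documents do not support them.

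- *That every seizure participant will in fact be treated and rescanned, so no untreated comparison exists.* Section 4.3 allows for some who never start or finish. That comparison exists, but it is self-selected and of unknown size, so it does not rescue the causal claim.
- *That the expected 50% responder rate could be mere chance.* The documents define neither a responder nor a typical seizure rate, and the 50% is a sample-size input. No chance rate can be derived without inventing both. A benchmark taken from each person's observed baseline count would also ignore regression to the mean, and would be undefined for anyone with no seizure in the baseline month. The entry criteria permit such people, since one seizure in the prior year suffices.
- *That the pilot trial's standard-care arm settles the matter, one way or the other.* Section 2.0 says of it "SMC showed no seizure reduction or improvement in any secondary outcomes". It gives no arm sizes or responder count, only 38 patients with PNES over four arms, roughly 9 to 10 each. It says nothing about PTE and is not named as a comparator here.
- *That imaging measures will regress to the mean.* Entry is on diagnosis and seizure history, not on fMRI signal, so this bias is plausible for seizure counts only.
- *That the false-attribution percentages are predictions.* They restate an assumed drift, and the plan's multiple-comparison correction would lower them.

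**Conclusion.** The point holds. As planned, the design can show whether imaging changes during CBT-Sz, whether that differs from rescan change in TBI controls, and whether it tracks clinical improvement. It cannot show that CBT-Sz caused the change, because treatment and seizure diagnosis coincide by plan. For seizure frequency the gap is complete.

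That conclusion rests on the design as described and needs no numerical assumption. The illustrative size (38% to 70% for the paired test and 22% to 42% against controls, rather than 5%) depends wholly on an assumed drift of 0.2 to 0.3 SD in seizure participants only. With no such drift both tests hold at 5%. Nothing here implies that CBT-Sz is ineffective, that the association between brain and clinical change is not worth studying, or that the trial needs another arm. It is a matter of matching the claim and its test to the design, and worth doing.

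**What to change.** 1. Reword Objective 3 and Hypothesis 2, in line with Specific Aim 2, as imaging change during CBT-Sz relative to rescan change in TBI controls, and the association of that change with clinical improvement.
2. In section 4, name the group-by-time contrast of PNES and of PTE against controls as the test of Hypothesis 2, in place of the pre/post test alone.
3. In the same section, state that this contrast corrects for rescan and practice effects only, and that neither imaging change nor seizure response will be reported as caused by CBT-Sz.
4. Describe the completer comparison in section 4.3 as exploratory and self-selected.

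No arm, visit or measurement is added. The costs are a weaker claim and less power than the paired test, as shown in step 4 of the working.

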#### **Study personnel:**

Study personnel will be responsible for recruiting, advertising, enrolling, obtaining informed consent, administering the protocol, assessments and surveys, maintaining the case report forms and data entry. The PIs and their designated staff will be responsible for quality assurance and total study oversight, as well as the adherence to the CBT-Sz sessions and imaging protocols. Study personnel will be trained in the study modalities and measures required for this protocol.

### **2.0 Introduction**

#### **Preliminary Studies**

#### **Cognitive Behavioral Therapy (CBT-Sz)**

The PIs have extensive expertise in diagnosis and treatment of seizures, and both have studied and published extensively in the field. The preliminary data from the PIs' studies that are described below provide the necessary preparation for both, the intervention and the neuroimaging aspects of this study. [name] work provides preliminary data for the efficacy of the intervention. [name] work provides the preliminary neuroimaging data. Both investigators have a long-standing history of collaboration including conducting the only randomized controlled trial of CBT for PNES.

CBT-Sz is used for both ES and PNES, and is based on initial studies conducted in patients with epilepsy as described below. We have systematically examined the clinical trial methodology in PNES: first in an open label study of sertraline for PNES, and then in a pilot placebo-controlled randomized controlled trial (RCT). We also modified a psychotherapy initially used in epilepsy for use in PNES or in epilepsy, and we completed an open label non-pharmacologic intervention. Next, we conducted a multi-center pilot RCT comparing CBT-Sz, sertraline, CBT-Sz and sertraline, and Standard Medical Care (SMC).

To describe CBT-Sz developed for this study, we focus on two of our completed treatment trials that demonstrated a significant reduction in PNES and improvement in comorbidities. The treatment is an approach predicated on the observation that in patients with seizures, life experiences and trauma

result in maladaptive core beliefs (negative schemas) and they demonstrate cognitive distortions and somatic symptoms. The 12 weekly, 1-hour long, individual therapy sessions are specifically tailored for patients with PNES or epilepsy to address directly both the seizures and the comorbidities that commonly occur in seizure disorders and to promote behavioral change, self-control, and self-efficacy. This approach has the advantage of being validated and manualized, facilitating its use and evaluation in multicenter studies. CBT-Sz addresses connections between mood, cognition and the environment, as well as patients' automatic thoughts, catastrophic thinking, maladaptive schemas, and somatic misinterpretations.

Based on positive preliminary results, we conducted a multi-site randomized controlled trial (RCT), where 38 patients with video/EEG-confirmed, lone PNES were randomized to one of four treatment arms: Medication (sertraline) only, CBT-Sz only, CBT-Sz and Medication combined, or standard medical care (SMC). The CBT-Sz arm showed >50% seizure reduction ( $p < 0.01$  with 33% of the participants seizure-free at study exit), improvement in functioning and in scores on symptoms scales. The combined treatment arm also showed improvements in seizures and functioning while the Medication arm showed a trend for seizure improvement. SMC showed no seizure reduction or improvement in any secondary outcomes. Similarly, the workbook-based therapeutic approach (CBT-E) showed reduction in patients with epileptic seizures. Given that the intervention has been validated and manualized, successfully disseminated to other sites, used in multi-center studies, and that it reduces seizures and comorbidities, this is the most logical next step to investigate its ability to induce cortical plasticity and a potential biomarker for treatment response.

## **Imaging**

The past neuroimaging studies in PNES and ES have documented only a single time point in small groups of participants; none of them assessed neurophysiological or clinical changes over time or in response to a specific behavioral challenge (CBT-Sz). In PNES, it is widely accepted that structural imaging should be normal, which is not always the case. While epidemiologic studies did not report specifically on imaging findings, other studies have found that up to 40% of patients with PNES have structural abnormalities on routine MRIs, which is similar to patients with PTE related to mild or moderate TBI. Thus, while only a few studies performed such analyses, it is clear that imaging abnormalities are frequent in patients with PNES, and may have negative implications for outcomes despite the fact that the lesions are not the direct cause of PNES.

## **Functional imaging in epilepsy and PNES**

Pathological responses to stressors are the origin of Conversion Disorders (CDs), which are thought to be related to “repression of psychological conflict and its conversion into physical” symptoms. Neuroimaging investigations of pathophysiologic mechanisms underlying CDs and PNES or epilepsy are scarce. In a motor CD study the authors explained the observed differences between patients with CD and comparable participants without CD as different utilization of emotion and stress neural circuits for processing stressful lifetime events. Another study showed greater FC between right amygdala and right supplementary motor cortex indicating a possible mechanism underlying motor CD. We recently compared emotion processing in patients with epilepsy and PNES without the preexisting TBI or without introducing an intervention ([name] et al., HBM under review). We have shown that compared to ES, that patients with PNES exhibit increased fMRI response to happy and neutral emotions in cerebellar and fronto-temporo-parietal regions and to fear in bilateral inferior and middle temporal gyri and right middle occipital gyrus. Connectivity analyses comparing patients with PNES and ES identified substantial differences in functional connectivity to several brain regions, particularly to cerebellar, visual, and fronto-temporal regions. Resting state connectivity of the left and right amygdala to various brain regions including emotion regulation circuits was increased in patients with PNES when

compared to patients with ES. Additional analyses showed aberrant functional connections between left uncus and right hemispheric regions in PNES compared to both the ES and healthy control groups. In summary, we documented that patients with PNES exhibit altered emotion processing and increased amygdala functional connectivity compared to ES. These findings identified key differences in emotion processing reflective of potential neurophysiologic markers of neural circuitry alterations in PNES with their presence possibly underlying initiation and/or maintenance of PNES when compared to ES.

